### 6.3.3.1 Additional follow-up for hepatic toxicities

Hepatic toxicity monitoring includes the following LFTs: albumin, ALT, AST, total bilirubin (fractionated if total bilirubin  $>$  2 x ULN), alkaline phosphatase (fractionated if alkaline phosphatase is grade 2 or higher) and GGT. For patients with Gilbert Syndrome: total and direct bilirubin must be monitored, intensified monitoring applies to changes in direct bilirubin only.

Close observation is recommended in case of AST, ALT, and/or bilirubin increase requiring dose interruption, which involves:

- Repeating liver enzyme and serum bilirubin tests **two or three times weekly**. Frequency of re-testing can decrease to once a week or less if abnormalities stabilize or return to normal values.

- Obtaining a more detailed history of current symptoms.
- Obtaining a more detailed history of prior and/or concurrent diseases.
- Obtaining a history of concomitant drug use (including non-prescription medications, herbal and dietary supplements), alcohol use, recreational drug use, and special diets.
- Ruling out acute viral hepatitis types A, B, C, D, and E; hepatotropic virus infections (CMV, EBV or HSV); autoimmune or alcoholic hepatitis; NASH; hypoxic/ischemic hepatopathy; and biliary tract disease.
- Obtaining a history of exposure to environmental chemical agents.
- Obtaining additional tests to evaluate liver function, as appropriate (e.g., INR, direct bilirubin).
- Considering gastroenterology or hepatology consultations.
- Assessing cardiovascular dysfunction or impaired liver oxygenation, including hypotension or right heart failure as possible etiologies for liver dysfunction.

**Table 6-5 Dose modification guidance in case of QT Prolongation**

Grade	Dose Modification
For all grades	
Check the quality of the ECG.
 
Perform analysis of serum electrolytes (K+, Ca++, Phos, Mg++). If below the lower limit of normal, interrupt ribociclib administration, correct with supplements or appropriate therapy as soon as possible, and repeat electrolytes until documented as normal.
 
Review concomitant medication usage for the potential to inhibit CYP3A4 and/or to prolong the QT interval.
 
Check compliance with correct dose and administration of ribociclib.

Grade 1 QTc 450-480 ms	No dose adjustment required.
Grade 2 QTc 481-500 ms	
Interrupt ribociclib
 
Perform a repeat ECG 1 hour after the QTcF of <math>\geq 481</math> ms
 
If QTcF <math><481</math> ms, restart ribociclib at the same dose. No dose adjustment required for first occurrence.
 
If QTcF remains <math>\geq 481</math> ms, repeat ECG as clinically indicated until QTcF returns to <math>< 481</math> ms. Restart ribociclib at the same dose level. No dose adjustments required for first occurrence.
 
If QTcF <math>\geq 481</math> ms recurs, ribociclib should be reduced by 1 dose level.
 
Repeat ECGs 7 days and 14 days after dose resumption (then as clinically indicated) for any patient who has therapy interrupted due to QTcF <math>\geq 481</math> ms.

Grade 3 QTc $\geq 501$ ms on at least two separate ECGs	
Interrupt LEE011
 
Consider consulting a local cardiologist
 
Perform a repeat ECG one hour after the first QTcF of <math>\geq 501</math> ms.
 
If QTcF remains <math>> 501</math> ms, repeat ECG as clinically indicated, but at least once a day until the QTcF returns to <math>< 481</math> ms.
 
If QTcF returns to <math>< 481</math> ms, ribociclib will be reduced by 1 dose level. Refer to Table 6-2 for dosing schedule.
 
Repeat ECGs 7 days and 14 days after dose resumption for any patient who had therapy interrupted due to QTcF <math>\geq 501</math> ms
 
If QTcF of <math>\geq 501</math> ms recurs, discontinue ribociclib

Grade	Dose Modification
Grade 4 [QT/QTc $\geq$ 501 or $>$ 60 ms change from baseline] and [Torsades de pointes or polymorphic ventricular tachycardia, or signs/symptoms of serious arrhythmia]	Discontinue ribociclib Obtain local cardiologist consultation Perform a repeat ECG 1 hour after the first QTcF of $\geq$ 501 ms If QTcF remains $\geq$ 501 ms, repeat ECG as clinically indicated, but at least once a day until the QTcF returns to $<$ 501 ms.

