Asymptomatic Grade 2 QTcF prolongation was observed with increasing frequency when increasing the dose starting at 600 mg: twelve patients (18%) in the 600 mg cohort, three patients (21%) in the 750 mg cohort, four patients (31%) in the 900 mg cohort, and two patients (67%) in the 1200 mg cohort. Two patients (3%) at 600 mg and two patients (15%) at 900 mg had asymptomatic QTcF prolongation that resulted in a QTcF interval of 500 ms or more. As compared to baseline value, QTcF prolongation was at least 30 msec in 2 patients (50%) at 250mg, 2 (40%) at 350 mg and 400 mg, 46 (73%) at 600 mg, 10 (71%) at 750 mg, 11 (85%) at 900 mg and 2 (67%) at 1200 mg; and at least 60 msec as compared to baseline in respectively 16%, 0%, 39% and 67% of patients at 600 mg, 750 mg, 900 mg and 1200 mg. One grade 1 atrioventricular block of first degree was reported as related to LEE011 given at the dose of 140 mg. No other cardiac abnormalities were observed as related adverse events in any patient.

There have been no deaths related to study drug reported on study [CLEE011X2101]. The following serious adverse events shown in Table 1-1 have been reported with a suspected causal relationship in study [CLEE011X2101] as of 19-Aug-2014. For a complete list of AEs, all grades and Grade 3/4 that are suspected to be related to LEE011 refer to the Investigator Brochure.

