#### 7.2.2.6 Cardiac assessments

##### 7.2.2.6.1 Electrocardiogram (ECG)

Standard triplicate 12 lead ECG assessments will be performed after the patient has been resting for 5-30 min prior to each time point indicated in [Table 7-2](#) below. The triplicate ECGs should be taken approximately 2 minutes apart. The combined QTcF values from triplicate ECGs will be averaged to provide a single value for each patient. If an abnormal ECG or QTcF value of  $\geq$  481 ms is obtained at any time during the study, study treatment must be interrupted, repeat the ECG measurements and follow management guidelines detailed in [Table 6-5](#).

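### Table 6-5 has no row for a single unconfirmed QTcF of 501 ms or more, and the steps of the two nearest rows end in opposite dose outcomes

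*Protocol*

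**What the plan says.** Protocol Table 6-5 sets its rows by QTc range: "Grade 1 QTc 450-480 ms", "Grade 2 QTc 481-500 ms", and grade 3 as 501 ms or more "on at least two separate ECGs".

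- **Grade 1 row:** no dose adjustment.
- **Grade 2 steps:** interrupt, then repeat the ECG an hour after a QTcF of 481 ms or more; no upper limit is given for that trigger. If the repeat is below 481 ms, "restart ribociclib at the same dose. No dose adjustment required for first occurrence". If 481 ms or more recurs, the dose goes down one level.
- **Grade 3 steps:** interrupt, then "Perform a repeat ECG one hour after the first QTcF of" 501 ms or more. If QTcF stays above 501 ms, keep repeating at least daily until it is below 481 ms. If it returns to below 481 "ms, ribociclib will be reduced by 1 dose level". If 501 ms or more recurs, ribociclib is discontinued.

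Protocol section 7.2.2.6.1 averages the triplicate QTcF values to one value per patient. It then says that if an abnormal ECG or a QTcF of 481 ms or more "is obtained at any time during the study, study treatment must be interrupted, repeat the ECG measurements", and it refers the site to Table 6-5. The note under Table 7-2 orders interruption only for QTcF of 481 ms or more.

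**The concern.** The grade 3 heading needs two ECGs, but the grade 3 steps begin after one. A site that sees one high value and a normal repeat has no row to work from, and it can support either of two dose decisions from the text. The choice carries forward: if the episode counted under the grade 3 row, a later value of 501 ms or more means permanent discontinuation; if it did not, that line may not apply.

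QTcF prolongation is one of the considerations given in protocol section 2.3 for choosing 600 mg, and section 12 permits no authorized deviations, so the rule has to be determinate. There is also a reporting side. The SAP tabulates dose reductions and interruptions with their reasons (3.5.1.5), reasons for discontinuing study drug (3.3), and QTc prolongation as an adverse event of special interest (5.1.5). Sites that read the table differently would produce counts that do not mean the same thing.

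**Working it through.** No sample size or error rate is involved. The check sets the row headings against the step texts for pairs of first QTcF and one-hour repeat. The grade 2 column applies that row's step trigger (481 ms or more) literally, without its heading.

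| First, ms | Repeat, ms | Heading met | Grade 2 step text | Grade 3 step text |
|---|---|---|---|---|
| 490 | 470 | Grade 2 | Same dose | Not triggered |
| 510 | 470 | None | Same dose | Reduce one level |
| 510 | 490 | None for the 510 | Repeat until below 481, then same dose | No instruction for this repeat |
| 510 | 501 | Grade 3 | Repeat until below 481, then same dose | No instruction: 501 is not above 501 |
| 510 | 510 | Grade 3 | Repeat until below 481, then same dose | Repeat until below 481, then reduce |

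Reading down the table:

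1. *510 then 470.* The first value is above the grade 2 range, and there is only one value for grade 3. No heading applies, and the two step texts end differently.
2. *510 then 490.* The grade 3 steps cover a repeat above 501 ms and a return to below 481 ms, but not the range between.
3. *510 then 501.* The heading (501 or more, twice) is met, but the repeat-daily step asks for a value above 501. The grade 4 row uses 501 or more for the corresponding step, so the inequality is not consistent within the table.
4. *Any first value of 450-480.* This is grade 1 and lies below the 481 ms trigger of section 7.2.2.6.1. The numeric thresholds do not overlap.

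Protocol section 6.3.1 bases modifications on the worst preceding toxicity grade, but it does not say how to grade one unconfirmed reading of 501 ms or more.

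**Exposure.** Inputs: in the first-in-human study, two patients (3%) at 600 mg "had asymptomatic QTcF prolongation that resulted in a QTcF interval of 500 ms or more" (protocol section 1.2.1.2.1); 106 patients enrolled (Amendment 3).

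- 0.03 × 106 = 3.18, about 3 patients.
- The share that would be single, unconfirmed readings is not given. Taking it from 0 to all, the range is 0 to about 3.
- The source figure includes values of exactly 500 ms, which fall in grade 2.

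**The case against.** The best defence is to read the grade 3 steps in sequence. The one-hour repeat is how the second ECG is obtained, and the return to below 481 ms picks up the end point of the preceding line, so the reduction would follow only a confirmed value. Section 6.3.1 supports letting the grade heading govern. This is a fair reading, and it removes the reduction for an unconfirmed value. It does not supply a row for that value, because grade 2 still stops at 500 ms.

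A reader might infer more than the documents support:

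- *That the table issues two competing orders for one reading.* It does not. The same-dose outcome is reached only by taking the 481 ms trigger from inside a row whose heading ends at 500 ms. The reading belongs to neither row.
- *That a repeat of 490 ms produces a contradiction.* The repeat itself lies in the grade 2 range. What is missing is a line in the grade 3 steps.
- *That tracings within one triplicate could count as two ECGs.* Section 7.2.2.6.1 averages them, and SAP 5.5 does the same. Table 6-5 would still be clearer if it said so.
- *That section 7.2.2.6.1 contradicts the grade 1 row.* This holds only if an abnormal ECG includes a QTc of 450-480 ms. That reading would make the separate 481 ms limb redundant. The grade 2 row also pairs interruption with no dose adjustment, so the latter phrase need not exclude interruption.
- *That many patients are exposed.* The 12 patients (18%) with grade 2 prolongation at 600 mg scale to 0.18 × 106 = about 19, but they have a clear row. The 46 patients (73%) whose QTcF rose by at least 30 ms show a change from baseline, not a grade 1 rate.

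It is also true that enrollment has closed and that one patient remained on study at Amendment 3.

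**Conclusion.** The point stands as a wording defect in one table, with a secondary ambiguity in one sentence. A single QTcF of 501 ms or more that is not confirmed has no row, and on the step texts the outcome could be the same dose or a one-level reduction, with discontinuation at the next event depending on whether this one counted. The missing 481-500 ms repeat and the mismatched inequality are plain on the page. The undefined abnormal-ECG limb is an ambiguity, not a demonstrated conflict.

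The number affected is small: at most about 3 of 106, and possibly none. This assumes that the first-in-human rate applies here and that all 106 were managed under the current table. The second assumption is generous, because Amendment 2 changed the QTc guidance when 78 patients had already been dosed. Section 1.2.1.2.1 does not say whether its values were single, repeated or averaged. The reason to correct the text is that a safety rule should give one answer, not that many patients are likely to meet the gap.

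**What to change.** Reconcile Table 6-5, section 7.2.2.6.1 and the Table 7-2 note:

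1. Give the grade 3 heading and its steps the same trigger and the same inequality.
2. After a first value of 501 ms or more, give one instruction for each repeat range: below 481 ms, 481-500 ms, and 501 ms or more.
3. State whether an unconfirmed first value counts when deciding if a later one is a recurrence.
4. State in the table that grading uses the triplicate mean already defined in section 7.2.2.6.1, and say what counts as a separate ECG.
5. Define abnormal ECG in section 7.2.2.6.1, or align that limb with Table 6-5 and the Table 7-2 note.

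Which dose action belongs in each case is for the sponsor to decide; this review takes no view on it. The cost is an amendment to the wording of one table and one sentence, checked against the table note. No additional ECGs are needed.

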### 6.3.3.2 Management of all other adverse reactions

Consider performing an analysis of serum potassium, calcium, phosphorus, and magnesium for all adverse reactions that are potentially associated with electrolyte imbalance (e.g. diarrhea, nausea/vomiting). If electrolyte values are below the lower limit of normal, interrupt ribociclib administration, correct electrolyte with supplements as soon as possible, and repeat electrolyte testing until documented normalization of the electrolytes.

**Table 6-6 Ribociclib dose adjustment and management recommendation for all other adverse reactions**

Grade	Dose Adjustment and Management Recommendations
1	No dose adjustment recommended. Initiate appropriate medical therapy and monitor.
2	Dose interruption until recovery to grade $\leq$ 1. Initiate appropriate medical therapy and monitor. Re-initiate LEE011 at the same dose. If the same toxicity recurs at grade 2, interrupt LEE011 until recovery to grade $\leq$ 1. Re-initiate LEE011 at the next lower dose level.
3	Dose interruption until recovery to grade $\leq$ 1. Initiate appropriate medical therapy and monitor. Re-initiate LEE011 at the next lower dose level. If toxicity recurs at grade 2: temporary dose interruption until recovery to grade $\leq$ 1 and reduce LEE011 dose the next lower dose level. If toxicity recurs at grade 3, discontinue LEE011.
4	Discontinue LEE011 and treat with appropriate medical therapy.

### 6.3.3.3 Adjustment of starting dose in special populations

#### Renal impairment

Insufficient data are available to provide a dosage to provide a dosage recommendation for ribociclib for patients with renal impairment. Patients with baseline renal impairment are excluded from the study (serum creatinine  $>$  ULN or creatinine clearance  $<$  50mL/min). Patients who experience renal impairment of grade 2 or higher during the treatment period should discontinue treatment and should be followed safety assessments.

#### Elderly

Physicians should exercise caution in monitoring the effects of ribociclib in the elderly. Insufficient data are available to provide a dosage recommendation.

### 6.3.4 Follow-up for toxicities

Patients who complete treatment or whose treatment is interrupted or permanently discontinued due to an AE must be followed at least once a week for 4 weeks, and then at 4

weeks intervals until resolution or stabilization of the event. All patients will be followed for onset of any new serious adverse events for 30 days following the last dose of study treatment.

### **6.3.5 Anticipated risks and safety concerns of the study**

Appropriate eligibility criteria, as well as specific dose modifications and stopping rules are included in this protocol. Refer to [Section 6.3.1](#) and [Section 6.3.2](#) for details.

## **6.4 Concomitant medications**

In general, the use of any concomitant medication/therapies deemed necessary for the care of the patient is permitted, except as specifically prohibited. Refer to LEE011 Investigator's Brochure and [Appendix A](#) for information on possible drug-drug interactions.

Patients must be instructed to not take additional medications (including over-the-counter products and herbal/alternative medications) during the study without prior consultation with the investigator.

Patients taking chronic medications should be maintained on the same dose and schedule throughout the study period, if medically feasible.

### **6.4.1 Permitted concomitant therapy**

Medications required to treat AEs, manage cancer symptoms, concurrent stable diseases and supportive care agents, such as packed red blood cells (PRBC), pain medications, anti-emetics and anti-diarrheals are allowed. The use of any other potential new concomitant medications may be discussed between the investigator and the sponsor on a case by case basis. Hematopoietic growth colony stimulating factors may be used therapeutically or as secondary prophylaxis.

The patient must be told to notify the investigational site about any new medications he/she takes after the start of study treatment. All medications (other than study drug) and significant non-drug therapies (including physical therapy, oxygen, and blood transfusions) administered to the patient within 30 days prior to the first dose of study drug, during the study, and until 30 days after the last dose of study drug, must be listed on the Concomitant Medications or the Procedures and Significant Non-Drug Therapies eCRFs.

#### **6.4.1.1 Bisphosphonates and denosumab**

Bisphosphonates and denosumab are permitted for the treatment of osteoporosis and prevention of skeletal related events for patients with bone metastases. Chronic concomitant bisphosphonate/denosumab therapy for the prevention of bone metastasis is not permitted.

#### **6.4.1.2 Palliative radiotherapy**

Palliative radiation is permitted if done solely for bone relief. It should not be delivered to a target lesion and it should not encompass more than 25% of irradiated bone marrow.

Refer to the ribociclib (LEE011) Investigator's Brochure, Table 1 and Table 2, for information on possible interaction with other drugs.

#### **6.4.2 Concomitant therapy requiring caution**

The following therapies are permitted in this study; however, they should be used with caution. This list is not comprehensive and is only meant to be used as a guide. These medications should be excluded from patient use if possible. If they must be given, then use with caution and consider a ribociclib interruption if the concomitant medication is only needed for a short time:

- Moderate inhibitors or inducers of CYP3A4/5
- Sensitive substrates of CYP3A4/5 with wide therapeutic index
- Sensitive substrates of the renal transporters, MATE1 and OCT2
- Sensitive substrates of BCRP
- Known inhibitors of BSEP
- Medications that carry a possible risk for QT prolongation

#### **6.4.3 Prohibited concomitant therapy**

The following medications are prohibited during treatment in this study ([Appendix A](#)). This list is not comprehensive and is only meant to be used as a guide:

- Strong inhibitors or inducers of CYP3A4/5
- Substrates of CYP3A4/5 with narrow therapeutic window
- Medications with a known risk for QT prolongation
- Other investigational and antineoplastic therapies
- Primary prophylactic hematopoietic growth factors
- Herbal medications. These herbal medications include, but are not limited to: St. John's wort, Kava, ephedra (ma huang), gingko biloba, dehydroepiandrosterone (DHEA), yohimbe, saw palmetto, black cohosh and ginseng. Patients should stop using all herbal medications at least 7 days prior to first dose of study treatment.
- Patients should be instructed not to take grapefruit products/juice, or Seville (sour) oranges/juice while taking study drug and preferably 7 days before the first dose due to potential CYP3A4/5 interaction. Oranges juice is allowed.

[figure not shown]
### **6.5 Patient numbering, treatment assignment and enrollment**

#### **6.5.1 Patient numbering**

Each patient is identified in the study by a Patient Number (Patient No.), that is assigned when the patient is first screened and is retained as the primary identifier for the patient throughout his/her entire participation in the trial. The Patient No. consists of the Center Number (Center No.) (as assigned by Novartis to the investigative site) with a sequential patient number suffixed to it, so that each Patient is numbered uniquely across the entire database. Upon signing the informed consent form, the patient is assigned to the next sequential Patient No. available at the site.

#### **6.5.2 Treatment assignment and randomization**

Not applicable.

### **6.5.3 Treatment blinding**

This is an open-label study.

## **6.6 Study drug preparation and dispensation**

The investigator or responsible site personnel must instruct the patient or caregiver to take the study drugs as per protocol. Study drug(s) will be dispensed to the patient by authorized site personnel only. All dosages prescribed to the patient and all dose changes during the study must be recorded on the Dosage Administration Record eCRF.

Patients will be provided with an adequate supply of study drug for self-administration at home, including instructions for administration, until at least their next scheduled study visit. Patients will receive ribociclib on an outpatient basis. The investigator shall provide the patient with instructions for ribociclib administration according to the protocol.

### **6.6.1 Study drug packaging and labeling**

Ribociclib will be supplied as 200 mg or 50 mg hard gelatin capsules (refer to [Table 6-6](#)).

Medication labels will comply with US legal requirements and are printed in the local language. The label contains LEE011 identifying information (e.g., formulation, batch number, and expiration date), the patient number (to be entered by the investigator or designee) and storage conditions.

**Table 6-6 Packaging and labeling**

Study treatments	Packaging	Labeling (and dosing frequency)
Ribociclib (LEE011)	Capsules or tablets (200 mg or 50 mg) in bottles or blisters	Labeled as LEE011 Dosing frequency: once-a-day, 3 weeks on/1 week off

### **6.6.2 Drug supply and storage**

Each site will be supplied by Novartis with oral ribociclib. Study drug must be received by a designated personnel at the study site, handled and stored safely and properly, and kept in a secured location to which only the investigator and designated site personnel have access.

Upon receipt, ribociclib should be stored according to the instructions specified on the drug labels and in the [Investigator's Brochure]. These instructions should also be made clear to the patient for storage and self-administration of ribociclib at home.

Site staff will be responsible for managing adequate re-supplies for ribociclib.

